3.2 Exclusion Criteria

- 3.2.1 Prior treatment with the following agents known to have endocrine effects on prostate cancer: GnRH agonist, GnRH antagonist, anti-androgen (bicalutamide, nilutamide, flutamide), ketoconazole, diethylstilbestrol, estrogen, abiraterone acetate. Concurrent use of 5α -reductase inhibitors finasteride or dutasteride is permitted for patients who have been already receiving either of these treatments for at least 1 month at the time of study enrollment. Baseline PSA must have been obtained in such patients after at least 1 month on 5α -reductase treatment. Initiation of treatment with 5α -reductase inhibitors is not permitted within the first 12 months of study participation.
- 3.2.2 Concomitant treatment with agents thought to have endocrine effects on prostate cancer: PC-SPES, saw palmetto
- 3.2.3 Treatment with corticosteroids within 4 weeks prior to enrollment.
- 3.2.4 Treatment with androgens within 6 months prior to study enrollment.
- 3.2.5 Subjects may not be receiving any other investigational agents. Concurrent enrollment in another clinical investigational drug or device study is prohibited.
- 3.2.6 Prostate cancer metastases to the bones, viscera, or non-regional lymph nodes (lymph nodes other than pelvic lymph nodes within the radiation treatment field)
- 3.2.7 Serum PSA > 160 ng/dL
- 3.2.8 History of malignancy (other than non-melanoma skin cancer) within 5 years of enrollment
- 3.2.9 Patients with histologic evidence of small cell carcinoma of the prostate will not be eligible.
- 3.2.10 Treatment for malignancy with anticancer therapy, including cytotoxic agents, hormonal agents, or immunotherapy, within 5 years of enrollment
- 3.2.11 History of allergic reactions attributed to compounds of similar chemical or biologic composition to *enzalutamide* or other agents used in this study.
- 3.2.12 Uncontrolled intercurrent illness including, but not limited to, ongoing or active infection, symptomatic congestive heart failure (> NYHA class II hear failure), unstable angina pectoris, cardiac arrhythmia, chronic active hepatitis, acute hepatitis, uncontrolled diabetes mellitus, or psychiatric illness/social situations that would limit compliance with study requirements.
- 3.2.13 Patients with any of the following within 6 months of enrollment: deep vein thrombosis, pulmonary embolus, myocardial infarction, cerebrovascular accident, unexplained loss of consciousness.

- 3.2.14 Patients with any history of seizure or seizure disorder.
- 3.2.15 Patients with medical conditions which, in the opinion of the investigators, would pose undue risk to the patient
- 3.2.16 Subjects unwilling to use contraceptives if they have sexual intercourse with a female partner of child-bearing potential while receiving treatment on this study.
- 3.2.17 Standard contraindications to MRI: For example, MRI non-compatile cardiac pacemakers, intracranial clips, foreign metal objects in the body and others as defined in the UT Southwestern Institutional MRI Safety Policy)
- 3.2.18 The following medications are prohibited during the study:
 - Substrates of CYP2B6, CYP2C8, CYP2C9, and CYP2C19 with a narrow therapeutic index, including paclitaxel, phenytoin, warfarin, omeprazole
 - Substrates of CYP3A4 with a narrow therapeutic index, including alfentanil, cyclosporine, dihydroergotamine, ergotamine, fentanyl, pimozide, quinidine, sirolimus, tacrolimus
 - Strong CYP2C8 inhibitors, including gemfibrozil
 - Strong CYP3A4/5 inhibitors, including clarithromycin, itraconazole, ketoconazole

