4.3 Concomitant Medications/Treatments

In vitro studies show that enzalutamide and/or metabolite M2 are potential inhibitors of CYP2C8 and CYP2C19 with lesser potential for inhibitory effects on CYP2B6 and CYP2C9. Enzalutamide is a moderate CYP2C9 and CYP2C19 inducer in humans. For this study, substrates of CYP2B6, CYP2C8, CYP2C9, and CYP2C19 that have a narrow therapeutic index (e.g., paclitaxel, phenytoin, warfarin, omeprazole) are prohibited.

In vitro studies show that enzalutamide is an inducer of CYP3A4. Induction of CYP3A occurs via activation of the nuclear pregnane X receptor (PXR), which is expected to result in co-induction of CYP2C. Co-administration of enzalutamide with CYP3A or CYP2C substrates may reduce oral bioavailability and/or accelerate elimination of these substrates. Enzalutamide is a strong CYP3A4 inducer in humans. For this study, concomitant use of enzalutamide with narrow therapeutic index drugs that are metabolized by CYP3A4 (e.g., alfentanil, cyclosporine, dihydroergotamine, ergotamine, fentanyl, pimozide, quinidine, sirolimus and tacrolimus) is prohibited.

In vitro studies show that enzalutamide is metabolized by CYP2C8 and CYP3A4/5. Strong inhibitors or inducers of these enzymes may affect enzalutamide exposures. Coadministration of a strong CYP2C8 inhibitor (gemfibrozil) increased the composite area under the plasma concentration-time curve (AUC) of enzalutamide plus N-desmethyl enzalutamide in healthy volunteers. For this study, co-administration of enzalutamide and strong CYP2C8 inhibitors (e.g., gemfibrozil) is prohibited. Co-administration of a strong CYP3A4 inhibitor (itraconazole) increased the composite AUC of enzalutamide plus Ndesmethyl enzalutamide by 1.3 fold in healthy volunteers. For this study, strong inhibitors of CYP3A4/5 (e.g., clarithromycin, itraconazole, ketoconazole) are prohibited during enzalutamide treatment.

Use caution when co-administering strong inducers of CYP2C8 (e.g., rifampin) or CYP3A4/5 (e.g., carbamazepine, phenytoin, rifampin, St. John's wort) during enzalutamide treatment, as enzalutamide concentrations may decrease.

In vitro studies show that enzalutamide and metabolite M2 are potential inhibitors of the efflux transporter P-gp. Co-administration of enzalutamide with P-gp substrates may increase the plasma concentrations of the P-gp substrate. Use caution when co-administering sensitive P-gp substrates (e.g., colchicine, dabigatran etexilate, digoxin) during enzalutamide treatment.

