7.0 ADVERSE EVENTS

7.1 Experimental Therapy

For the most recent safety update, please refer to the current Investigator's Brochure or Study Agent Prescribing Information.

7.1.1 Contraindications: Enzalutamide is contraindicated in pregnancy.

7.1.2 Special Warnings and Precautions for Use: Seizure occurred in 0.9% of patients who received enzalutamide in a completed phase III trial. There is no clinical trial experience with enzalutamide in patients who have had a seizure, in patients with predisposing risk factors for

seizure, or in patients using concomitant medications that may lower the seizure threshold. Patients with a history of seizure or with predisposing risk factors for seizure are ineligible to participate in this study.

7.1.3 Interaction with other medications:

In vitro studies show that enzalutamide and/or metabolite M2 are potential inhibitors of CYP2C8 and CYP2C19 with lesser potential for inhibitory effects on CYP2B6 and CYP2C9. Enzalutamide is a moderate CYP2C9 and CYP2C19 inducer in humans. For this study, substrates of CYP2B6, CYP2C8, CYP2C9, and CYP2C19 that have a narrow therapeutic index (e.g., paclitaxel, phenytoin, warfarin, omeprazole) are prohibited during the period of enzalutamide administration.

In vitro studies show that enzalutamide is an inducer of CYP3A4. Induction of CYP3A occurs via activation of the nuclear pregnane X receptor (PXR), which is expected to result in co-induction of CYP2C. Co-administration of enzalutamide with CYP3A or CYP2C substrates may reduce oral bioavailability and/or accelerate elimination of these substrates. Enzalutamide is a strong CYP3A4 inducer in humans. For this study, narrow therapeutic index drugs that are metabolized by CYP3A4 (e.g., alfentanil, cyclosporine, dihydroergotamine, ergotamine, fentanyl, pimozide, quinidine, sirolimus and tacrolimus) are prohibited.

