In vitro studies show that enzalutamide is metabolized by CYP2C8 and CYP3A4/5. Strong inhibitors or inducers of these enzymes may affect enzalutamide exposures. Coadministration of a strong CYP2C8 inhibitor (gemfibrozil) increased the composite area under the plasma concentration-time curve (AUC) of enzalutamide plus N-desmethyl enzalutamide in healthy volunteers. For this study, co-administration of enzalutamide and strong CYP2C8 inhibitors (e.g., gemfibrozil) is prohibited. Co-administration of a strong CYP3A4 inhibitor (itraconazole) increased the composite AUC of enzalutamide plus Ndesmethyl enzalutamide by 1.3 fold in healthy volunteers. For this study, coadministration of enzalutamide and strong inhibitors of CYP3A4/5 (e.g., clarithromycin, itraconazole, ketoconazole) are prohibited.

Use caution when co-administering strong inducers of CYP2C8 (e.g., rifampin) or CYP3A4/5 (e.g., carbamazepine, phenytoin, rifampin, St. John's wort) during enzalutamide treatment, as enzalutamide concentrations may decrease.

In vitro studies show that enzalutamide and metabolite M2 are potential inhibitors of the efflux transporter P-gp. Co-administration of enzalutamide with P-gp substrates may increase the plasma concentrations of the P-gp substrate. Use caution when co-administering sensitive P-gp substrates (e.g., colchicine, dabigatran etexilate, digoxin) during enzalutamide treatment.

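### Sections 4.3 and 7.1.3 each both prohibit phenytoin and allow it with caution, and two restatements of the co-medication ban set a shorter period than 3.2.18

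*Combined protocol and SAP*

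**What the plan says.** The protocol states its co-medication rules in three places.

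Section 3.2.18, within the exclusion criteria, introduces four classes with "The following medications are prohibited during the study". The classes are narrow-index substrates of CYP2B6, 2C8, 2C9 and 2C19; narrow-index CYP3A4 substrates; strong CYP2C8 inhibitors; and strong CYP3A4/5 inhibitors. Phenytoin is named in the first class. Sections 4.6 and 5.3 keep subjects on study to 12 months (48 weeks), while enzalutamide stops at about 6 months (24 weeks, section 5.2).

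Section 4.3, on concomitant medication, restates the classes with varying scope. For the CYP2B6/2C substrates the rule is "narrow therapeutic index (e.g., paclitaxel, phenytoin, warfarin, omeprazole) are prohibited", with no period. For CYP3A4 substrates what is banned is "concomitant use of enzalutamide with narrow therapeutic index drugs that are metabolized by CYP3A4". For CYP2C8 inhibitors: "For this study, co-administration of enzalutamide and strong CYP2C8 inhibitors (e.g., gemfibrozil) is prohibited". For CYP3A4/5 inhibitors: "For this study, strong inhibitors of CYP3A4/5 (e.g., clarithromycin, itraconazole, ketoconazole) are prohibited during enzalutamide treatment".

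Section 7.1.3, on interactions, uses the same drugs with different scope. The CYP2B6/2C rule ends "e.g., paclitaxel, phenytoin, warfarin, omeprazole) are prohibited during the period of enzalutamide administration". The CYP3A4 substrate rule has no period: "dihydroergotamine, ergotamine, fentanyl, pimozide, quinidine, sirolimus and tacrolimus) are prohibited". The CYP2C8 inhibitor sentence is the same as in 4.3, and the CYP3A4/5 inhibitor rule reads "coadministration of enzalutamide and strong inhibitors of CYP3A4/5 (e.g., clarithromycin, itraconazole, ketoconazole) are prohibited".

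Both 4.3 and 7.1.3 then advise caution with strong inducers of CYP2C8 or CYP3A4/5 during enzalutamide treatment, because enzalutamide levels may fall. Phenytoin is one of the named CYP3A4/5 examples.

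**The concern.** Two things look wrong.

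First, advice to be cautious when giving phenytoin with enzalutamide presupposes that the two may be given together. The same section has already said that they may not. The conflict lies inside 4.3 and again inside 7.1.3, so reading either section in full does not settle it.

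Second, 3.2.18 is a rule for conduct on study, but it sits among criteria applied at registration. Months later, a clinician asked to prescribe a new drug would more naturally open the section on concomitant medication or the one on interactions. Some of the wording there ends the ban with enzalutamide.

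At stake is a patient starting a narrow-index drug too soon after the last capsule. Warfarin is a plausible case: section 8.2 lists thrombosis among the effects seen with GnRH analogs, and leuprolide continues after enzalutamide stops. Section 4.3 describes enzalutamide as a strong CYP3A4 and a moderate CYP2C9/2C19 inducer in humans that may lower exposure to CYP3A and CYP2C substrates.

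**Working it through.** **Phenytoin.** It is prohibited by name in 3.2.18, 4.3 and 7.1.3, and named in the caution list in 4.3 and 7.1.3. In 7.1.3 the prohibition and the caution cover the same period, enzalutamide treatment. In 4.3 the prohibition has no period and so includes the time to which the caution applies. The conflict is present in 2 of 2 sections. Phenytoin is 1 of the 17 drugs named in 3.2.18 (4 + 9 + 1 + 3 across the four classes).

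**Period of the ban.** Four classes in two sections give 4 × 2 = 8 restatements to set against the whole-study period in 3.2.18.

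| Class | Section 4.3 | Section 7.1.3 |
|---|---|---|
| CYP2B6/2C substrates | no period | explicit, shorter |
| CYP3A4 substrates | use together | no period |
| Strong CYP2C8 inhibitors | use together | use together |
| Strong CYP3A4/5 inhibitors | explicit, shorter | use together |

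Explicitly shorter: 2 of 8. Worded as use together with enzalutamide: 4 of 8. No period: 2 of 8. The total is 2 + 4 + 2 = 8. The explicit difference from 3.2.18 is 48 − 24 = 24 weeks on study.

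**Does the shorter period matter for substrates?** Section 1.2.2 gives a half-life of about 5.8 days, steady state after about one month, and steady-state exposure 8.3 times that of a single dose. After 24 weeks of dosing a subject is at steady state. Assuming mono-exponential decline of parent drug, the fraction remaining at day t is 2^(−t/5.8):

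- day 7: 2^(−7/5.8) = 0.433, about 43%
- day 14: 2^(−14/5.8) = 0.188, about 19%
- day 28: 2^(−28/5.8) = 0.035, about 3.5%

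Time to fall to the exposure of one single dose: 5.8 × log2(8.3) = 17.7 days.

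Parent drug therefore persists for weeks after use together has formally ended. The documents give no human figure for the active metabolite M2 or for how fast induction wears off; either could lengthen this interval.

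**Does it matter for inhibitors?** The stated reason for banning both inhibitor classes is increased exposure to enzalutamide and its N-desmethyl metabolite; for itraconazole the stated increase is 1.3-fold. Once dosing has stopped, an inhibitor could slow the decline but adds no drug. The documents give no figure and describe no hazard for that situation.

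**The case against.** The strongest reply on the period is that the rules nest. The 3.2.18 ban covers every shorter one, and section 11.4 requires the study to be conducted as the protocol describes, so a compliant team has one answer. Each substrate class also has an unqualified ban in one of the other two sections: CYP2B6/2C substrates in 4.3, CYP3A4 substrates in 7.1.3. To start warfarin early, someone would have to miss both 3.2.18 and 4.3. This stands, and it limits the period part to a risk from reading one section alone.

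A reader might infer that six of the eight restatements time-limit the ban. The text does not support that: only two state a period. The other four name a pair of drugs not to be combined and give no start or stop, so taking them to permit use the day after the last capsule is one reading, not the stated rule.

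A reader might also infer that gemfibrozil or clarithromycin is a hazard straight after the last dose. The protocol's own rationale, higher enzalutamide exposure, does not carry over to the time after dosing.

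Nor do the documents support a particular washout, such as five half-lives (5 × 5.8 = 29 days). That is a convention based on parent drug alone and appears nowhere in the protocol. The text directly after the interaction paragraphs of 7.1.3 was also not available, so I do not claim that 7.1.3 lacks a washout; 4.3, which is complete, states none.

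On phenytoin, the caution sentence concerns a different effect, lowered enzalutamide levels, and practical reach is small. Any seizure history excludes a patient (3.2.14), waivers are not permitted (3.0), a seizure on study leads to removal (4.2), and the planned size is only seven or ten subjects (study summary and section 10.2). The reach argument stands. It does not remove the contradiction, because caution in co-administration still implies permission.

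**Conclusion.** The text is wrong as written, but the point is minor. The phenytoin conflict is certain from the wording and occurs in both sections. The period inconsistency is explicit in two of eight restatements and possible on one reading in four more. Its practical consequence is confined to staff who rely on 4.3 or 7.1.3 alone, and mainly to narrow-index substrates in the weeks after the last dose. That last judgement rests on the half-life in section 1.2.2, mono-exponential decline, and the protocol's description of enzalutamide as a CYP inducer; how long induction lasts is not documented. It would be too strong to say that the plan gives irreconcilable instructions on the period, or that subjects are exposed to risk throughout the remaining six months on study. No sample size, endpoint definition or analysis is affected.

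**What to change.** Remove phenytoin from the caution examples in 4.3 and 7.1.3 and leave the prohibition as it is. In the same two sections, state the whole-study period of 3.2.18 for all four prohibited classes.

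If the sponsor prefers a shorter ban, write one period in identical words in 3.2.18, 4.3 and 7.1.3, with any washout length set by the sponsor from its own data on parent drug, M2 and the offset of induction.

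The cost is wording in two sections (three under the alternative), an update to any concomitant-medication list drawn from them, and the IRB approval that section 11.5 requires for an amendment. No visit, procedure or analysis is added.

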4.0 TREATMENT PLAN

4.1 Treatment Dosage and Administration

- 4.1.1 We propose a single-institution, single-arm study of neo-adjuvant, concomitant, and adjuvant enzalutamide plus GnRH agonist with external beam radiation therapy for the treatment of patients with high-risk and locally-advanced prostate cancer.
- 4.1.2 Eligible study participants will receive treatment with enzalutamide 160 mg daily for 6 months in combination with GnRH agonist treatment. Following the initial two months of treatment with enzalutamide and GnRH agonist, radiation therapy will be administered as detailed below. GnRH agonist treatment will be continued for a total treatment duration of 24 36 months at the discretion of the treating physician in concert with the patient. Treatment will be administered on an outpatient basis.

Table 4.1 Agent	Dose	Route	Schedule
Enzalutamide	160 mg daily (four 40 mg capsules)	p.o.	Daily for 6 months
Leuprolide acetate	22.5 mg every 3 months	IM	Every 3 or 6 months (depending on dosage
	or		form used) for a total treatment duration of
	45 mg every 6 months		24-36 months

A study medication diary will be provided to each subject in which daily oral selfadministration of enzalutamide will be documented. If a dose is missed, enzalutamide should be resumed the next day at the established daily dose of 160 mg. A vomited dose should not be replaced.

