1.2.2 Summary of human experience with enzalutamide (MDV3100)

The pharmacokinetics (PK), tolerability, and antitumor activity of MDV3100 were first studied in a multi-center, open-label, first-in-human, dose-escalation study of MDV3100 in 140 patients with castration-resistant prostate cancer (S-3100-1-01).¹⁰ Patients who were chemotherapy-naïve or who had previously failed docetaxel-based chemotherapy were treated with MDV3100 at doses of 30 to 600 mg/day until disease progression or intolerable side effects developed.

MDV3100 was absorbed rapidly after oral administration, with the time to maximum plasma concentration (tmax) after a single dose typically occurring at 1 hour postdose. No major deviations from dose proportionality were observed over the dose range 30 to 600 mg. Due to the long t1/2 (~ 5.8 days), it took approximately 1 month to reach steady state. With daily oral administration MDV3100 accumulation was observed at steady

state with an 8.3-fold higher exposure (steady-state area under the curve [AUC]) relative to a single dose. Based on the mean peak-to-trough ratio, the average difference between the peak (Cmax) and trough (minimum plasma concentration [Cmin]) concentrations was $\leq 25\%$. As a result of the low daily fluctuations, plasma profiles at steady-state resembled a constant infusion. The Cmin values in individual patients remained constant beyond Day 28 of chronic therapy, suggesting time-linear PK once steady state was achieved.

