4.2 Toxicities and Dosing Delays/Dose Modifications

Any subject who receives treatment on this protocol will be evaluable for toxicity. Each patient will be assessed for the development of toxicity according to the Time and Events table (Table 5.4). Toxicity will be assessed according to the NCI Common Toxicity Criteria for Adverse Events (CTCAE), version 4.0. Dose adjustments should be made according to the system showing the greatest degree of toxicity.

Enzalutamide (Xtandi, MDV3100) has been shown to be well-tolerated when used in combination with androgen deprivation (in the form of GnRH agonists or castration by orchiectomy) in completed phase I, II, and III clinical trials.

Та	ble 4.2.1 Hematological To	oxicity Dose Reductions for Enzalutamide
ANC	Platelets	Action
≥ 1,500/µL	100,000/μL	None.
1000-1499/μL	75,000-99,000/μL	 -1st Occurrence:Hold current dose until ANC ≥ 1,500/µL and platelets ≥ 100,000/µL. Do not replace missed doses. Restart next treatment at 120 mg dose. -2nd Occurrence:Hold current dose until ANC ≥ 1,500/µL and platelets ≥ 100,000/µL. Do not replace missed doses. Restart next treatment at 80 mg dose. -3rd Occurrence: Discontinue protocol therapy.
500-999/μL	50,000-74,000/μL	 -1st Occurrence:Hold current dose until ANC ≥ 1,500/µL and platelets ≥ 100,000/µL. Do not replace missed doses. Restart next treatment at 120 mg dose. -2nd Occurrence: Discontinue protocol therapy.
<500/μL	<50,000/μL	-1st Occurrence: Discontinue protocol therapy.

Table 4.2.2. Non-hematological Toxicity Dose Reductions		
NCI CTC Grade	Enzalutamide	
0-2	No change from original starting dose (with the exception of seizure)	
3-4	Hold until resolved to	
Second episode of	Hold until resolved to <grade 2,="" 80="" dose<="" mg="" reduce="" td="" then="" to=""></grade>	
grade 3 or 4 toxicity		
Third episode of	Remove subject from trial	
grade 3 or 4 toxicity		

In the randomized clinical trial of patients with docetaxel-refractory metastatic CRPC, 7 of 800 patients (0.9%) treated with enzalutamide 160 mg daily experienced a seizure. No seizures occurred in patients treated with placebo. Patients experiencing seizures were permanently discontinued from therapy and all seizures resolved. There is no clinical trial experience re-administering enzalutamide to patients who experienced seizures. Therefore, should a subject experience any seizure, enzalutamide will be discontinued and the subject removed from the trial.

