8.0 DRUG INFORMATION

8.1 Enzalutamide

- Other names for the drug: Xtandi, MDV3100
- Classification type of agent: oral androgen receptor inhibitor
- Mode of action: inhibits androgen-induced receptor activation (binding of androgens to ARs in the cytosol), inhibits nuclear translocation of activated ARs, and inhibits the association of the activated AR with chromatin
- Storage and stability: Enzalutamide capsules should be stored at 20 C to 25 C (68 F to 77 F) in a dry place. Excursions are permitted from 15 C to 30 C (59 F to 86 F).
- Protocol dose: Subjects will take four 40 mg capsules (160 mg) daily. Patients will be given one bottle of 120 capsules at every 4 week follow up visit.
- Route of administration for this study: oral

- Availability: provided by sponsor free of charge
- Side effects: Adverse events associated with enzalutamide that are most likely to occur in this study include asthenia/fatigue, back pain, diarrhea, arthralgia, hot flush, peripheral edema, musculoskeletal pain, headache, upper respiratory infection, muscular weakness, dizziness, insomnia, lower respiratory infection, hematuria, paresthesia, anxiety, and hypertension. Please refer to the Xtandi (enzalutamide) package insert for a comprehensive list of adverse events.
- Nursing implications:

8.2 GnRH agonist – For the purposes of this study we are only using Lupron. Additonal GnRH agonists are listed below for informational purposes only.

• Description: GnRH agonists are long-acting analogs of the native GnRH peptide and are effective at reducing serum testosterone. Analogs approved by the FDA.

- Supply: Commercially available.
- Storage: GnRH analogs should be stored as directed by the commercial supplier.

• Administration: GnRH analogs are administered with a variety of techniques, including subcutaneous insertion of a solid plug in the abdominal wall (Zoladex), intramuscular injection (Lupron), subcutaneous injection (Eligard), or insertion of a long-acting cylinder that slowly

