8.2.1 Return and Retention of Study Drug

Unused study drug (enzalutamide) will be documented and returned to the Simmons Comprehensive Cancer Center Pharmacy for destruction per Standard Operating Procedures

8.2.2 Subject compliance with the study agent, enzalutamide, will be monitored through use of a pill diary provided to each subject enrolled in the study. A new pill diary will be provided at every 4 week follow up visit for the duration of the administration of enzalutamide on the study.

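### The missed-dose rule in Section 4.1.2 resumes enzalutamide at 160 mg and makes no exception for a patient already reduced for toxicity

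*Combined protocol and SAP*

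**What the plan says.** Section 4.1.2 sets enzalutamide at 160 mg daily for six months, self-administered and recorded in a diary. It adds: "If a dose is missed, enzalutamide should be resumed the next day at the established daily dose of 160 mg". The next sentence, "A vomited dose should not be replaced", does not mention reduced doses either.

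Section 4.2 provides for reductions. In Table 4.2.1 a first occurrence in the mildest abnormal row (ANC 1000-1499 or platelets 75,000-99,000) leads to a hold and then "Restart next treatment at 120 mg dose". A second occurrence restarts at 80 mg and a third stops therapy. The next row (ANC 500-999 or platelets 50,000-74,000) reads, after the hold, "Restart next treatment at 120 mg dose. -2nd Occurrence: Discontinue protocol therapy". Below that, therapy stops at once. In Table 4.2.2 a second grade 3-4 non-hematological episode reduces the dose to 80 mg. Its grade 0-2 row reads "No change from original starting dose (with the exception of seizure" and does not refer to the dose the patient is then taking.

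On supply, Section 8.1 restates four capsules (160 mg) a day and says: "Patients will be given one bottle of 120 capsules at every 4 week follow up visit". Section 8.2.2 says: "A new pill diary will be provided at every 4 week follow up visit".

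**The concern.** The missed-dose sentence names a number, not the patient's own dose. A man reduced to 120 mg or 80 mg who forgets a day, and who follows the sentence, goes back to the dose that preceded his toxicity. No available sentence says that a reduction persists, bars re-escalation, or puts Section 4.2 above Section 4.1.2. Section 11.4 requires the study to be run as the protocol describes, so staff who sensibly resume 120 mg are departing from Section 4.1.2. What is at stake is the safety of the few patients who have already shown they do not tolerate full dose.

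**Working it through.** **1. Which rule applies.** Section 4.2 covers the restart after a toxicity hold. A patient who has already restarted at 120 mg and later simply forgets a day is not in a hold, so the only instruction that addresses him is the 160 mg sentence.

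**2. Change in daily dose.** 160/120 = 1.33 (+33%); 160/80 = 2.00 (+100%).

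**3. Change in exposure.** Inputs from Section 1.2.2: a half-life of about 5.8 days, and "No major deviations from dose proportionality were observed over the dose range 30 to 600 mg". I use a one-compartment model with daily dosing. The fraction remaining after a day is k = 2^(-1/5.8) = 0.887. Model accumulation is 1/(1 - k) = 8.9, against the 8.3-fold that Section 1.2.2 reports, so the model is adequate here. Start at steady state on the reduced dose, skip one day, then take 160 mg for n days. With r = 160/(reduced dose), the ratio to the reduced-dose steady state is r + (k - r) × k^n.

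| Days at 160 mg | k^n | From 120 mg (r = 1.333) | From 80 mg (r = 2) |
|---|---|---|---|
| 1 | 0.887 | 0.94 | 1.01 |
| 7 | 0.433 | 1.14 | 1.52 |
| 28 | 0.035 | 1.32 | 1.96 |

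How long 160 mg would continue is an assumption; 1 to 28 days spans one visit interval.

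**4. Time at risk.** With counts every 4 weeks, an event at week 4 that has recovered by week 8 restarts at 120 mg with 24 - 8 = 16 weeks of drug left. A second event at week 12, recovered by week 16, restarts at 80 mg with 24 - 16 = 8 weeks left.

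**5. Supply.** A 28-day interval needs 4 × 28 = 112 capsules at 160 mg, 3 × 28 = 84 at 120 mg and 2 × 28 = 56 at 80 mg. A bottle of 120 therefore allows full dose until the next visit, whatever dose is assigned.

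**6. Restart doses in Section 4.2.** The protocol does not say whether occurrences in Table 4.2.1 are counted within each row or pooled. Call its two reducing rows mild and moderate.

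- Counted by row, eight sequences leave the patient on drug: mild (120 mg), moderate (120), mild-mild (80), mild-moderate (120), moderate-mild (120), mild-mild-moderate (120), mild-moderate-mild (80) and moderate-mild-mild (80). The last step is no reduction in two (mild-moderate, moderate-mild) and an increase in one (mild-mild-moderate, 80 to 120 mg).
- Pooled, four remain on drug: mild (120), moderate (120), mild-mild (80) and moderate-mild (80). None stays level or rises.
- Across tables: 80 mg after a second grade 3-4 non-hematological episode, then a first hematological occurrence, restarts at 120 mg (120/80 = 1.5, or +50%).

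On scheduled counts alone, the mild-mild-moderate path has its third event at week 20 and recovery at week 24, when enzalutamide ends, so no time is spent at the raised dose.

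**The case against.** The best reply is that Section 4.2 must already override the missed-dose sentence. Table 4.2.1 calls held doses missed, says they are not made up, and restarts them at 120 or 80 mg. It also speaks of holding the current dose, so the protocol recognises a dose other than 160 mg. Otherwise Section 4.1.2 would cancel every hold the next day. This stands as evidence of intent. It does not reach the ordinary missed day after a restart, which is left to a sentence that names 160 mg.

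Second, Section 4.4.1.8 has patients seen weekly during radiotherapy. By Section 5.2 that runs from weeks 8-10 to roughly weeks 16-20, much of the time at risk. No dose check is prescribed at those visits, but they make a 28-day error less likely, and correction within a week holds the ratios to 1.14 and 1.52. Section 8.2.1 also requires unused drug to be documented and returned, and the bottle leaves spare capsules even at 160 mg. The supply therefore shows only that dispensing does not block the error.

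Third, a reader might infer that Table 4.2.1 itself commonly raises doses. It does not: within a row the dose only falls, the one within-table increase needs a counting rule the protocol does not state, and one in eight is a count of possible sequences, not a frequency.

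**Conclusion.** The missed-dose instruction is wrong for a reduced patient as written, and should be corrected as a minor patient-safety point. Its size is +33% or +100% in daily dose. Exposure is close to unchanged after one day, about 1.14 or 1.52 times the reduced-dose steady state after 7 days, and at most 1.32 or 1.96 times after 28. These ratios assume the stated half-life, dose proportionality and a patient already at steady state on the reduced dose; a miss soon after restarting would give less. The Section 4.2 gap matters only in the rare paths shown.

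Three stronger readings are not supported. A reader might infer that patients would be overdosed, but no path exceeds the approved 160 mg (Section 1.2), and Sections 4.5, 5.5 and 11.4.1 let the investigator stop or deviate for safety. A reader might infer that reversals are likely in this study, but the documents give neither an adherence figure nor the number of patients who will need a reduction. A reader might infer that no protecting sentence exists anywhere, but some pages were not available and one cell of Table 4.2.2 is cut off in the text, so the statement is limited to what can be read. The descriptive safety analysis is unchanged.

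**What to change.** In Section 4.1.2, replace the fixed 160 mg in the missed-dose sentence with the patient's currently assigned dose, and make the same change in the diary if it repeats the rule.

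As a secondary safeguard, add to Section 4.2 that the restart dose is the lower of the table dose and the dose at onset, with no re-escalation after a toxicity reduction. Keep every existing discontinuation rule. Counting by row, this changes one of the eight on-drug sequences (mild-mild-moderate ends at 80 mg, not 120 mg) and no discontinuation; it also closes the cross-table path. How occurrences are counted, and whether a moderate event at 120 mg should lead to 80 mg or to stopping, is for the sponsor and investigator to settle.

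The cost is two sentences in one amendment, with no new visits, data or patients.
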